We are planning to conduct this study in patients with a cutaneous melanoma (T3a, T3b, T4a, T4b, N0 or N+, M0, Stage IV with no evidence of M+ disease), that have undergone curative surgical treatment and will not undergo (neo)adjuvant treatment. The product that we are going to use in this trial, WholeFiber™, is hypothesized to influence the microbial composition in a way that specific microbes, which are reported to produce SCFA, are favored on short term^{16,19}. The goal of the study is to test the effect of the inulin rich dietary fiber without any conditions that are hypothesized to influence its effects^{24,25}. The proposed amount of 20 g has been used in previous studies using WholeFiber™, where no adverse effects were reported²⁶.

1.5 Future perspectives: moving towards advanced melanoma treated with immune checkpoint inhibitors

The discovery of the link between the gut microbiome, diet and response to immune checkpoint inhibitors (ICI) in stage IV melanoma patients have shown that the gut microbiome is not only a biomarker for treatment response but can also be a modifiable treatment target^{27,28}. Interestingly, the immune system plays an important role in patients with melanoma tumors.

What is unclear, and in our view should be the first small step and the objective of this study, is to determine whether changes in the gut microbiome in this group of patients (with skin melanoma) is possible at all, if these changes in the gut microbiome lead to an increased production of SCFA and whether the changes in gut microbiome; immune cell composition and SCFA can indeed be measured.

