2. OBJECTIVES

The primary objective of this study is to investigate the effect of dried chicory root (WholeFiberTM) for 6 weeks on fecal SCFA levels in intermediate to high-risk melanoma patients after surgical treatment with no concurrent adjuvant treatment.

Secondary objectives

- Exploration of the gut microbial composition of surgically treated intermediate to high-risk cutaneous melanoma patients before intake and potential compositional changes after using WholeFiberTM for 6 weeks.
- Exploration of the effect of WholeFiberTM use for 6 weeks on immune cell composition, stool patterns, fecal calprotectin levels and side effects in intermediate to high-risk cutaneous melanoma patients after surgical treatment, with no concurrent adjuvant treatment.

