8. METHODS

8.1. Study parameters

8.1.1. Main study parameter

Effect of a high fiber prebiotic vegetable (WholeFiber™) for 6 weeks on fecal SCFA levels in intermediate to high-risk cutaneous melanoma patients, with no concurrent adjuvant treatment. HPLC ion chromatography system (Metrohm AG, Herisau, Switzerland) will be used to determine the levels of SCFA. The concentrations of SCFA; butyrate, propionate, and acetate will be measured with a conductivity detector. SCFA will be measured at baseline, halfway intervention and after 6 weeks.

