8.3.6. Analyses of fecal material

Collected tubes with feces samples will be stored (at -80°C) until a sufficient batch size is present for further analyses (calprotectin, microbiome, SCFAs). Analyses of the microbiome will be conducted within the UMCG following standardized procedures. The composition and function of the gut microbiome will be analyzed prior to, mid-trial, and after the WholeFiber™ intervention using whole genome sequencing. Temporal changes in the gut microbiome following the WholeFiber™ intervention can be traced up to species and even strain level by using novel algorithms³³. Analyses and interpretation of the microbiome will be in the context of patient characteristics (age, sex, BMI), and use of medication, including vitamins, probiotics, and homeopathic compounds.

HPLC ion chromatography system (Metrohm AG, Herisau, Switzerland) will be used for the short chain fatty acid analysis. The concentrations of SCFA (acetic acid, propionic acid, butyric acid, isobutyric acid, valeric acid, isovaleric acid, 2-methylbutyric acid, caproic acid) will be measured with a conductivity detector. The 6.1005.200 Metrosep Organic Acids column (Metrohm AG) with 5mm particle size and dimensions of 7.8 mm by 250 mm will be used for differentiating fatty acids. The mobile phase is 5mM HNO₃ and acetonitrile v/v ratio of 98:2, respectively, with a flow rate of 0.6 ml per minute.

Fecal calprotectin levels will be measured in the collected fecal samples (baseline, mid-trial, end of intervention) using Enzyme-Linked Immuno Sorbent Assay (ELISA).

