10. STATISTICAL ANALYSIS

Statistical analyses will be performed using R. In general, continuous data will be presented as mean \pm standard deviation (SD) or median and interquartile range when skewed, and categorical data as counts and percentages. To correctly model the paired pre-post study design, we will use a linear mixed-effects model (*lme4*-package, version 1.1-35.2, Bates et al., 2015). This is performed by adding a patient-specific intercept and slope. As this is an exploratory study, mean differences with a 95% confidence interval will be considered as statistically significant. A false discovery rate (FDR) of 5% will be used in regression analyses, regarding SCFA and bacterial taxa, to correct for multiple testing. We will adjust for differences in age, sex, BMI, and fiber intake before the start of the intervention by including these as independent variables in the linear mixed-effects models described below.

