10.1. Primary study parameter(s)

This study population consists of one group, where the primary endpoint is defined as the effect of WholeFiber™ for 6 weeks on fecal SCFA levels in surgically treated intermediate to high-risk cutaneous melanoma patients with no concurrent adjuvant treatment. The study is considered to have a positive outcome when paired differences are measured in fecal SCFA levels, comparing pre- and post-intervention. This will be analyzed using a linear mixed-effects model, modeling the fecal SCFA levels post-intervention as the dependent variable and fecal SCFA levels pre-intervention together with patient-specific intercepts and slopes to take paired sampling into account. To further study the role of the gut microbiota, the relationship between post-intervention fecal SCFA levels and gut microbiota composition will be tested using a similar linear mixed-effects model. In this model, the post-intervention fecal SCFA levels will be modeled as the dependent variable and relative abundance of specific bacterial species together with patient-specific intercepts and slopes as independent variables.

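### The only model linking SCFA to gut bacteria compares levels between patients, so it does not test whether microbiome changes go with SCFA changes

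*Protocol*

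**What the plan says.** **The question.** The rationale in the Summary and section 1.5 describe what "should be the first small step and the objective of this study, is to determine whether changes in the gut microbiome" are possible in these patients, and then "if these changes in the gut microbiome lead to an increased production of SCFA". Section 1.5 calls this the objective. Section 2 is narrower: "The primary objective of this study is to investigate the effect of dried chicory root" on fecal SCFA, and no link between SCFA and microbiota is listed there.

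**The model.** Section 10.1 states that "the relationship between post-intervention fecal SCFA levels and gut microbiota composition will be tested using a similar linear mixed-effects model". The next sentence specifies it: "the post-intervention fecal SCFA levels will be modeled as the dependent variable and relative abundance of specific bacterial species", together with patient-specific intercepts and slopes, are on the two sides of the equation. Section 10 adds covariates to all the models: "We will adjust for differences in age, sex, BMI, and fiber intake before the start of the intervention".

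**The data.** Section 8.1.1: "SCFA will be measured at baseline, halfway intervention and after 6 weeks". Section 8.3.6: "The composition and function of the gut microbiome will be analyzed prior to, mid-trial, and after the" intervention. Both variables are therefore available for each patient at T0, T1 and T2.

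**The concern.** The stated question is about change within a patient: when a patient's bacteria shift, does that patient's SCFA shift too? The model relates a level to a level. Neither baseline SCFA, baseline abundance, visit nor change is among its terms.

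Patients differ in SCFA and in bacterial composition for lasting reasons such as habitual diet, transit time or medication. Age, sex, BMI and prior fiber intake capture only part of this. What they leave behind produces an association between levels even if nothing moves together during the intervention. A species could then be reported as tied to the SCFA response when it only marks patients who always have high SCFA. Conversely, a true link between changes can be swamped by stable differences. Section 13.1 says effects seen here would be taken into a large randomized trial, so a wrong species signal could carry forward.

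**Working it through.** **1. Which models could answer the question?**

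| Model | Outcome | Named predictors | Links SCFA change to microbiome change? |
|---|---|---|---|
| 10.1, first | post SCFA | pre SCFA | No, bacteria absent |
| 10.1, second | post SCFA | species abundance, visit not named | No, levels only |
| 10.2 | post abundance | pre abundance | No, SCFA absent |

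Only the second model contains both variables, and it contains no change.

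**2. Do the patient-specific terms rescue it?** If only T2 counts as post-intervention, there are 20 rows for 20 × 2 = 40 random intercepts and slopes, and the intercept cannot be separated from residual error. If T1 and T2 both count, there are 40 rows for 40 random effects, baseline still does not enter, and the single abundance coefficient mixes between-patient and within-patient association. The other models in 10.1 and 10.2 share this structural defect.

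**3. Size.** The protocol gives no figure to reproduce and no variances, so everything here is illustrative. Assumptions: n = 20, three visits, normal data, abundance taken at T2.

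- Species: X = a + e + visit shift.
- SCFA: Y = b + β_B·a + β_W·e + u + visit shift.
- SD(a) = SD(b) = 1; SD(e) = SD(u) = 0.6.
- Var(X) = 1 + 0.36 = 1.36.

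*No within-patient link* (β_W = β_B = 0; a and b correlated ρ). The correlation of T2 levels is ρ/1.36. Approximate rejection follows from Fisher's z with √17 = 4.12.

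| ρ | Level correlation | Approximate rejection | Simulated, no covariates |
|---|---|---|---|
| 0.36 | 0.26 | 20% | 21% |
| 0.49 | 0.36 | 34% | 35% |
| 0.64 | 0.47 | 56% | 58% |

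With four covariates, simulated rejection at the three values of ρ depends on how much of the shared patient factor they explain:

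- none: 16/28/48%
- a quarter: 12/21/35%
- half: 8/13/21%

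A within-patient regression over three visits rejects in 4–6% throughout.

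With the planned 5% FDR over an assumed 100 species, 20 of them sharing the patient factor, at least one discovery occurs in 16/33/58% of trials without covariates and in 9/14/29% with covariates explaining a quarter. The within-patient analysis gives 4–6%.

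*True within-patient link* (β_W = 0.5; a and b uncorrelated).

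- Levels: covariance = β_B + 0.5 × 0.36 = β_B + 0.18; Var(Y) = 1 + β_B² + 0.09 + 0.36.
- For β_B = 0 the correlation is 0.18/√(1.36 × 1.45) = 0.13; for 0.25 it is 0.43/√(1.36 × 1.5125) = 0.30; for 0.5 it is 0.68/√(1.36 × 1.70) = 0.45.
- T0-to-T2 change on change: 0.36/√(0.72 × 0.90) = 0.45, whatever β_B is.
- Within-patient, three visits: SE = 0.6/√(19 × 2 × 0.36) = 0.162, so the expected ratio is 0.5/0.162 = 3.1.

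| Analysis | Simulated power, raw p<0.05, β_B = 0/0.25/0.5 |
|---|---|
| Levels, no covariates | 9/26/53% |
| Levels, four covariates | 7/20/43% |
| Change on change | about 53% throughout |
| Within-patient, three visits | 83–84% throughout |

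**4. A second set of assumptions.** Patient SD 1, measurement-error SD 0.2, SD of change 0.3/0.5/1.0, T2 level on T2 level without covariates. With stable levels correlated 0.6 and changes unrelated, the levels test rejects in 71/57/24% of runs and the change test in about 5%. With changes correlated 0.6 and stable levels unrelated, the levels test rejects in 6/8/24% and the change test in 29/55/76%. The direction is the same.

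**The case against.** **The model matches the aim given for it in 10.1**, which is itself worded as a relationship with post-intervention levels, and the change question is not in section 2. This is true, and it limits the severity. But the Summary and section 1.5 do pose the change question, section 1.5 calls it the objective, and no other model addresses it.

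**A mixed model described as similar suggests repeated rows, and power then looks better.** A random-intercept model with visit terms and undivided abundance, on the same variances without covariates, has power 71/86/94% with rows from T0 to T2 and 39/64/81% with T1 and T2. So the risk of missing a real link depends on the reading. Using T0 rows, however, conflicts with an outcome defined as post-intervention. The false-positive problem persists on both readings: 16/28/43% and 17/31/54%.

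**Similar could mean that baseline SCFA is carried over.** The sentence listing the predictors omits it. Adding it lowers false positives to 6–14%, but power is then only 10–21%, and the predictor is still a level.

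**The power comparison flatters the replacement.** This is partly right. When β_B = β_W = 0.5, the levels model without covariates matches change on change at about 53%. The 83–84% is at raw p<0.05; at p<0.0005, the first Benjamini-Hochberg step for 100 species, within-patient power is about 27%. The data are simulated as normal although relative abundance is not.

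**The replacement does not prove causation and removes the average shift.** Both are correct and should be stated in the plan.

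**The visit for abundance can be left to the SAP.** Agreed; that omission alone is no finding. The point rests on the outcome and predictors that 10.1 does fix.

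**Conclusion.** The concern holds. The protocol asks about linked changes, and its only linking model compares levels. That follows from the text and needs no assumption. The size does: with no within-patient link, the levels model without covariates is falsely positive in 21–58% of trials for patient-level correlations of 0.36 to 0.64, and in 8–48% with covariates explaining from half to none of the shared factor, against about 5% for a within-patient analysis. Inflation appears on every reading examined. Loss of power is less certain, because it depends on which rows enter and on the between-patient slope.

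The model should be changed, but it does not threaten the trial: the analysis is exploratory, the link is not a section 2 objective, and the success criterion in 10.1 does not use this model.

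**What to change.** Replace the second model in section 10.1 by a model of SCFA at T0, T1 and T2 with:

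- visit as a categorical term;
- each species' abundance split into the patient's mean and the visit's deviation from that mean;
- the four covariates of section 10;
- a patient random intercept only.

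The coefficient on the within-patient deviation is the test, with the planned 5% FDR across species and SCFAs. Regressing T0-to-T2 change in SCFA on T0-to-T2 change in abundance is a simpler alternative, but it is less powerful and discards T1.

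State two limits. Visit terms absorb the average shift, so the test concerns differences between patients in how they change; the average shift stays with the pre-post models. In a single arm, the result shows that changes are associated, not that one causes the other.

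Cost: analysis wording and slightly more analysis work. No additional samples, visits or patients are needed.

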10.2. Secondary study parameter(s)

To analyze changes in gut microbiota in surgically treated intermediate to high-risk cutaneous melanoma patients using WholeFiber™ for 6 weeks, we will use a similar linear mixed-effects model as described above. In this model, the relative abundance of bacterial species post-intervention will be used as the dependent variable and their relative abundance pre-intervention together with patient-specific intercepts and slopes as independent variables. Furthermore, the effect of WholeFiber™ for 6 weeks on the microbial diversity will be evaluated using both alpha and beta diversity metrics. Alpha diversity metrics quantify within sample diversity and can be compared across groups. Beta diversity compares between sample diversity and is often calculated by computing a dissimilarity index (e.g. Bray-Curtis).

10.3. Other study parameters

Other study parameters such as anthropometry data or data from medical records will not be statistically tested but is used to describe the study population.

11. ETHICAL CONSIDERATIONS

11.1. Regulation statement

The study will be conducted in accordance with this protocol as well as the principles of the Declaration of Helsinki (64th WMA general assembly; October 2013), the ICH-GCP guidelines and other applicable laws and regulations, and in accordance with the principles of the Medical Research Involving Human Subjects Act (WMO). The study will start after approval of the medical ethical committee (METc) is obtained. The investigators in this study declare to have no conflict of interest.

11.2. Recruitment and consent

All participants are recruited from the UMCG. Also, patients who participated in earlier research projects may be re-invited. Patients who seem to meet the inclusion criteria are invited by their treating physician to consider participation. The researcher decides if the patient can make a well-informed decision. The primary investigator provides information to the patient using the PIF and arranges a first inclusion visit with the patient (either on site or virtual). The patient is given 2 weeks to consider participation. During this time, the patient is encouraged to consult for advice using various sources. After one-week, additional questions can be answered and if the patient opts to participate the informed consent is signed. Documented informed consent must be obtained from all patients prior to inclusion in the study. Informed consent will be asked in writing, and in the following manner: the patient will sign and personal date the informed consent form first. When the investigator has signed and dated the consent form afterwards, the patient will receive a copy. Finally, the general physician of each patient will be informed about the enrolment of the patient to the study by a standard letter. The informed consent procedure takes place conform Good Clinical Practice (GCP). Documented informed consent must be obtained from all subjects prior to inclusion in the study. All subjects will be informed about their right to withdraw their agreement at any time without resulting in any claim of damage and about the possibility to ask for supplementary information from an independent physician.

11.3. Benefits and risks assessment

Participating in this study has a potential health benefit. It is known that an increased intake of fiber has a positive effect on the abundance of beneficial bacteria. In patients with melanoma, it is hypothesized that there's an imbalance in the bacterial composition in the gut, leading to a reduction in beneficial bacteria. If melanoma patients experience a rise in beneficial bacteria, making the gut microbial composition more like the microbiome of healthy people, it may result in a more favorable disease outcome (reduced reoccurrence of the removed cutaneous melanoma).

Participants could experience some bloating or flatulence, which are GI symptoms that are generally related to an increased fiber intake, when they start with WholeFiber™. These discomforts are limited to the first few days of use and should not last longer than a few hours per day. In the previous clinical trials, using 30 g of the product, the participants did not report any major AEs in any of the study visits. The collection of feces and blood samples entails no risks for the subjects.

11.4. Compensation for injury

The investigator has a liability insurance, which is in accordance with article 7, subsection 6 of the WMO. The sponsor(s) (also) has/have an insurance, which is in accordance with the legal requirements in the Netherlands (Article 7 WMO and the Measure regarding Compulsory Insurance for Clinical Research in Humans of 23rd June 2003). This insurance provides cover for damage to research subjects through injury or death caused by the study.

1. € 450,000 (i.e. four hundred and fifty thousand Euro) for death or injury for each subject who participates in the Research;
2. € 3,500,000 (i.e. three million five hundred thousand Euro) for death or injury for all subjects who participate in the Research;
3. € 5,000,000 (i.e. five million Euro) for the total damage incurred by the organization for all damage disclosed by scientific research for the Sponsor as 'verrichter' in the meaning of said Act in each year of insurance coverage.

The insurance applies to the damage that becomes apparent during the study or within 4 years after the end of the study.

Note: an exemption for the insurance obligation, due to the negligible risk of this study is requested.

11.5. Incentives

Travel costs will be compensated: the subjects will receive a compensation of 0.21 euro/km when travelling by car. In addition, participants will receive a ticket for free parking at the UMCG on study days. The total amount of money will be paid after completing the study, and after the last samples have been collected. The dietary supplement will be given to the participant free of charge. Participating in the study will not result in costs for the participant.

12. ADMINISTRATIVE ASPECTS, MONITORING AND PUBLICATION

12.1. Handling and storage of data and documents

The handling of personal data complies with the Dutch 'GDPR (General Data Protection Regulation) and AVG (Algemene Verordening Gegevensbescherming). All related documents and records will be kept and archived for at least 15 years. The collection and processing of participants' personal information will be limited to what is necessary to ensure the study's scientific practicability, the evaluation of efficacy, adherence, side effects and the investigational product's safety. Information collected about participants during this clinical investigation will be treated confidentially. The investigator or her co-workers will collect data and transfer it without recording the patient's name or date of birth. Instead, data will be coded with a participant identification number. This identification number consists of the study name and the participant number (e.g. MELFIB-001, MELFIB-002, etc.).

The file with the key to the code will be managed by one person. The source documents will be kept in a locked file cabinet with limited access of the research personnel. In accordance with national laws and guidelines and the specifications of the ICH-GCP guidelines, the investigators are obligated to archive all documents pertaining to the study for the legally required period.

The acquired data and examination results will be entered into an electronic case record form (eCRF) that is accessible via the internet. Investigators will receive personal usernames and passwords for this purpose, and data will be encrypted for transfer. It will be agreed before the start of the study which documents serve as source documents for all data included in the eCRF.

12.2. Monitoring and quality assurance

Associated investigators will be carefully selected and comprehensively informed and trained regarding Good Clinical Practice (GCP), all study procedures and the required examinations and documentation.

The quality of data acquisition will be confirmed by regular monitoring visits as described in the Monitoring Plan. The monitor is independent from the study team and is not involved in the inclusion of participants and the design and implementation of the study. All monitoring activities will be in line with national laws and guidelines and the specifications of the ICH-GCP guidelines.

According to the NFU Richtlijn Kwaliteitsborging Mensgebonden Onderzoek (versie September 2023) this study can be identified as a low-risk study. Study monitors will visit the study site minimal once per year of which a minimal of two visits have to be on-site during the research period. Monitors will have access to all documents that are needed to perform their task according to the above-mentioned guidelines. Monitors will check whether requirements to conduct the study are met and study procedures are followed correctly, and will check the study site's documentation, the participants' source data, eCRF entries, and the correct maintenance of the Investigator Site File. Investigators will permit trial-related monitoring, audits, ERB reviews and regulatory inspections, providing direct access to source data and study documents.

